#### 8.10.1.3 *Prophylaxis Against Risk of Infection*

Patients may be at an increased risk of infection, including reactivation of herpes zoster and herpes simplex viruses. Prophylactic antiviral therapy such as acyclovir or valacyclovir should be initiated as clinically indicated. Please also see Sections 8.1.1.5 and 8.1.2.5.

### 8.10.2 Combination Agent

Please refer to the product labels for daratumumab SC ([Darzalex Faspro \(daratumumab and hyaluronidase-fihj\) 2022](#)) for the management of product related clinical events.

On days when both daratumumab SC and modakafusp alfa are administered, please refer to product label for daratumumab SC for the management of IRR events when they occur after daratumumab SC administration and before modakafusp alfa administration.

### 8.11 Blinding and Unblinding

This is an open-label study.

### 8.12 Description of Investigational Agents

Modakafusp alfa and the combination agent daratumumab SC are described in Sections 4.1.2 and 4.1.3.1. Further details on modakafusp alfa may be found in the IB.

### 8.13 Preparation, Reconstitution, and Dispensation

Parenteral drug products should be inspected visually for particulate matter and discoloration before administration whenever solution and container permit.

Modakafusp alfa is an anticancer agent, and as with other potentially toxic compounds, caution should be exercised when handling modakafusp alfa.

Please refer to the pharmacy manual for the preparation of each dose of modakafusp alfa.

Please refer to the respective package insert for the preparation of daratumumab SC.

### 8.14 Packaging and Labeling

Any sponsor-provided drugs will be labeled according to the current ICH guidelines on GCP and Good Manufacturing Practices and will include any locally required statements.

Modakafusp alfa is supplied as sterile, lyophilized powder in a single-use, 20R stoppered glass vial with an aluminum flip-off seal, on reconstitution providing 10 mg/mL (50 mg) of modakafusp alfa.

Details for daratumumab SC and other comparator agents are provided in the respective package insert for each agent.

## **8.15 Storage, Handling, and Accountability**

### **8.15.1 Modakafusp Alfa**

Modakafusp alfa must be stored according to the manufacturer's stipulation in a dry place and at temperature as stated on the product labeling.

The investigator or designee must confirm that appropriate temperature conditions have been maintained for all modakafusp alfa received and that any discrepancies are reported and resolved before the use of modakafusp alfa.

Each site shipment will include a packing slip listing the contents of the shipment, or any applicable forms.

The investigator is responsible for ensuring that deliveries of modakafusp alfa and other study materials from the sponsor are correctly received, recorded, handled, and stored safely and properly in accordance with the Code of Federal Regulations (CFR) or national and local regulations, and used in accordance with this protocol.

Only subjects enrolled in the study may receive modakafusp alfa and only authorized staff at the investigational center may supply or administer modakafusp alfa. All modakafusp alfa must be stored in a secure, environmentally controlled, and monitored (manual or automated) location in accordance with labeled storage conditions or appropriate instructions with access limited to the investigator and authorized staff at the investigational center.

The investigator, institution, or head of the medical institution (where applicable) is responsible for modakafusp alfa accountability, reconciliation, and record maintenance (ie, receipt, reconciliation, and final disposition records).

A record of modakafusp alfa accountability (ie, modakafusp alfa and other study materials received, used, retained, returned, or destroyed) must be prepared and signed by the principal investigator or designee, with an account given for any discrepancies. Empty, partially used, and unused modakafusp alfa will be disposed of, retained, or returned to the sponsor or designee.

If there is a discrepancy in product storage or handling between the protocol and other protocol related documentation, the product label shall supersede.

Further guidance and information are provided in the pharmacy manual.

### **8.15.2 Combination Agent**

The combination agent (daratumumab SC) should be stored at temperatures in accordance with the instructions provided in the manufacturer's product label and information in the pharmacy manual. Additional details are provided in the respective package insert for each agent.

If there is a discrepancy in product storage or handling between the protocol and other protocol related documentation, the product label or commercial package (as applicable) shall supersede.

## 9.0 STUDY CONDUCT

This study will be conducted in compliance with the protocol, GCP, applicable regulatory requirements, and ICH guidelines.

### 9.1 Study Personnel and Organizations

The contact information for the project clinician for this study, the central laboratory and any additional clinical laboratories, the coordinating investigator for each member state/country, and other vendors such as the contract research organization may be found in the study manual. A full list of investigators is available in Takeda's investigator database.

For 24-hour contact information, please refer to the study manual or equivalent.

### 9.2 Arrangements for Recruitment of Patients

Recruitment and enrollment strategies for this study may include recruitment from the investigator's local practice or referrals from other physicians. If advertisements become part of the recruitment strategy, they will be reviewed by the institutional review board (IRB)/ independent ethics committee (IEC).

### 9.3 Informed (e)Consent

Each patient must provide written or electronic informed consent before any protocol-directed procedures are conducted, unless those procedures are performed as part of the patient's standard care.

Patients consenting electronically (eConsent), where available, will electronically sign consent forms. Paper consent forms will be used instead if required by local regulations.

eConsent provides the same information as written consent forms, but in an electronic format that may include multimedia components. eConsent does not replace the important discussion between the study participant and site staff or investigator. Regardless of the consent format, the investigational site is responsible for the consenting process.

The requirements of informed consent are described in Section 15.2.

### 9.4 Treatment Group Assignments

During the phase 1 dose escalation, patients will be enrolled according to a rolling six design (see Section 8.4). During the phase 2a dose finding, patients will be randomized in a 1:1 ratio to treatment across 2 dose levels of modakafusp alfa in combination with daratumumab SC.

Randomization will be stratified (see Section 6.1).

In phase 2a, the window allowed between randomization to Cycle 1 Day 1 dosing is 3 days.

### 9.5 Study Procedures

Refer to the SOEs (Appendix A) for timing of assessments. Additional details are provided as necessary in the sections that follow.

### **9.5.1 Patient Demographics**

The date of birth or age, race, ethnicity, and sex of the patient are to be recorded during screening as permitted by local regulations.

### **9.5.2 Medical History**

During the screening period, a complete medical history will be compiled for each patient. This includes initial diagnosis date, MM staging at initial diagnosis using the Revised International Staging System. Known cytogenetic alterations should be also collected. Prior treatment regimens, with each treatment duration (start and stop dates), and the best response obtained with each of them. Refractoriness to previous treatments should be collected following IMWG criteria. For patients who have received previous anti-CD38 treatment, the worst grade of IRR should be recorded. In addition, concomitant medications will be recorded.

### **9.5.3 Physical Examination**

A physical examination will be completed per standard of care at the times specified in the SOEs ([Appendix A](#)).

If an investigator considers it safe and appropriate for a subject to miss a protocol-specified physical examination for coronavirus disease 2019 (COVID-19)-related reasons, the study site physician or other qualified site staff will speak directly with the subject by telephone or other medium (eg, a computer-based video communication) to assess subject safety and overall clinical status with a plan for in-person evaluation if signs and symptoms warrant. Such instances will be documented in the study records and eCRF if applicable, and the sponsor will be informed.

### **9.5.4 Patient Height and Weight**

Height will be measured during the screening visit only. Weight will be measured at the times specified in the SOEs ([Appendix A](#)).

### **9.5.5 Vital Signs**

Vital signs include temperature, pulse, respiratory rate, oxygen saturation, and blood pressure. They include also supine or seated measurements of diastolic and systolic blood pressure (after 3 to 5 minutes in this position; all measurements should be performed in the same initial position). They will be measured at the times specified in the SOEs ([Appendix A](#)). Vital signs will be measured at any time a patient complains of symptoms consistent with IRR or clinically indicated. If the patient experiences hypotension (with or without symptoms), intensive blood pressure monitoring according to local practice should be instituted. The patient cannot be released from the site until blood pressure has returned to Grade 1 or baseline for at least 1 hour. Patients must be observed for at least 2 hours after the end of the infusion of modakafusp alfa in each cycle when modakafusp is administered.

Any vital sign value that is judged by the investigator as clinically significant will be recorded both on the source documentation and the eCRF as an AE and monitored as described in Section 10.2.

#### **9.5.6      Pregnancy Test**

Participants of childbearing potential must have 2 negative pregnancy tests before starting study drug. A urine or serum pregnancy test will be required during screening and at baseline (within 72 hours before the start of study drug). A participant of childbearing potential is defined as a reproductive female who (1) has not undergone a hysterectomy or bilateral oophorectomy or (2) has not been naturally postmenopausal (amenorrhea following cancer therapy does not rule out childbearing potential) for at least 24 consecutive months (ie, has had menses at any time in the preceding 24 consecutive months).

During the study, participants of childbearing potential must have a negative urine or serum pregnancy test result within 72 hours before dosing on Day 1 of each cycle during treatment before dosing. Pregnancy tests may also be repeated during the study per request of the IRB or if required by local regulations.

At EOT, a urine or serum pregnancy test is required in participants of childbearing potential.

#### **9.5.7      Concomitant Medications and Procedures**

Any prior or concomitant medication a patient has had from signing of the ICF through 30 (+10) days after the last dose of study drug treatment (modakafusp alfa and/or daratumumab SC) or the start of subsequent systemic anticancer therapy, whichever occurs first, will be recorded on the eCRF. Trade name and international nonproprietary name (if available), indication, and start and end dates of the administered medication will be recorded. Medications used by the patient and therapeutic procedures (including any transfusion) completed by the patient will be recorded in the eCRF. See Sections 8.7 and 8.8 regarding medications and therapies that are prohibited or allowed, respectively, during the study.

#### **9.5.8      ECOG Performance Status**

ECOG performance status ([Appendix F](#)) will be evaluated and recorded as specified in the SOEs ([Appendix A](#)).

#### **9.5.9      AEs**

Monitoring of AEs, serious and nonserious, will be conducted throughout the study as specified in the SOEs ([Appendix A](#)). Refer to Section 10.0 for details regarding definitions, documentation, and reporting of AEs and SAEs.

#### **9.5.10     Enrollment**

Procedures for completing enrollment information are described in the study manual.

Rescreening is permitted if deemed appropriate by the investigator upon consultation with the sponsor when a patient might meet all the eligibility criteria with the cause(s) of previous screening failure being resolved.

### 9.5.11 ECG

A 12-lead ECG will be obtained at the time points specified in [Appendix A](#). A qualified person will interpret the ECG locally. Additional ECGs may be obtained as clinically indicated at the discretion of the investigator.

Any ECG finding that is judged by the investigator as clinically significant (except at the screening visit) will be considered a TEAE, recorded on the source documentation and in the eCRF, and monitored as described in Section [10.3](#).

### 9.5.12 Clinical Laboratory Evaluations

Clinical laboratory evaluations will be performed locally.

In extenuating circumstances, such as during the COVID-19 public health emergency, laboratories closer to a patient's home may be used for local clinical laboratory assessments provided that pertinent laboratory information, including normal reference ranges, are provided to the sponsor or designee.

#### 9.5.12.1 *Clinical Chemistry, Hematology, Urinalysis and Indirect Antiglobulin Test (Coombs Test)*

Blood samples will be obtained for analysis of clinical chemistry, hematology, and urinalysis as shown in [Table 9.a](#), [Table 9.b](#), and [Table 9.c](#), respectively. Samples will be obtained at time points as specified in the SOEs ([Appendix A](#)).

**Table 9.a Clinical Chemistry**

Albumin	Standard C-reactive protein
Alkaline phosphatase	Chloride
Alanine aminotransferase	Glucose (nonfasting)
Aspartate aminotransferase	Lactate dehydrogenase
Bilirubin (total)	Magnesium
Blood urea nitrogen	Phosphate
Calcium	Potassium
Bicarbonate ( $\text{HCO}_3^-$ ) or carbon dioxide ( $\text{CO}_2$ )	Sodium
Creatinine	Urate

If creatinine clearance is to be estimated, the Cockcroft-Gault formula will be used as follows:

Estimated creatinine clearance

$$= [(140 - \text{Age}) * \text{weight(kg)}] / [72 * \text{serum creatinine(mg/dL)}]$$

For female patients, the result of the formula above should be multiplied by 0.85.

**Table 9.b Hematology Tests**

Hematocrit	Leukocytes with differential a
Hemoglobin	Neutrophils (ANC)
Platelet count	

ANC: absolute neutrophil count.

aDifferential to include basophils, eosinophils, lymphocytes, monocytes, and neutrophils.

**Table 9.c Urinalysis**

Bilirubin	pH
Glucose	Protein
Ketones	Specific gravity
Leukocytes	Turbidity and color
Nitrites	Urobilinogen
Occult blood	

Urine microscopy will be performed if urinalysis is abnormal. Microscopy consists of RBC/high-power field, white blood cell/high-power field, casts, bacteria, and crystals.

Other clinical laboratory tests are outlined in [Table 9.d](#).

**Table 9.d Other Laboratory Tests**

Serum $\beta_2$ microglobulin	Blood type, Rh factor and indirect antiglobulin test (indirect Coombs test)
Thyroid function test (TSH, T4, T3)	Hepatitis B serology
HBV DNA test	

HBV: hepatitis B virus; Rh: Rhesus; T3: triiodothyronine; T4: thyroxine; TSH: thyroid stimulating hormone/thyrotropin.

### **9.5.13 Disease Assessment**

Unless otherwise specified as detailed in the SOEs ([Appendix A](#)), response assessment for phase 1 dose escalation and phase 2a dose finding will be made locally. Disease assessment will be conducted per the SOEs ([Appendix A](#)) and evaluated according to IMWG criteria ([Appendix E](#)).

In extenuating circumstances, such as during the COVID-19 public health emergency, patients may use an alternative site for imaging with prior notification to the sponsor or designee.

Serum and urine response assessments will be performed as indicated in the SOE ([Appendix A](#)).

Imaging tests for qualifying patients are to be performed every 12 weeks beginning with Cycle 3 only for patients with extramedullary disease at screening or when there is a clinical suspicion of extramedullary progression. Investigators will assess disease response/status. Response and relapse categories are described in [Appendix E](#).

CR should be confirmed with follow-up assessments of bone marrow aspirate (BMA), SPEP, UPEP, immunofixation of blood and urine, and serum FLCs as outlined in [Appendix A](#). One bone marrow assessment (locally) is required to document a CR; no second bone marrow confirmation is needed. At the time of collecting BMA samples to confirm CR locally, a BMA sample will be also collected for central analysis of MRD as the first pull.

Please note that to determine a response of sCR, bone marrow immunohistochemistry or immunofluorescence for the  $\kappa:\lambda$  ratio, as well as serum FLC assay, should be performed for all patients suspected to be in CR to meet this response category's requirements.

The disease assessments outlined in the following sections will be performed as shown in the SOEs ([Appendix A](#)).

#### 9.5.13.1 *Extramedullary Disease Imaging*

Imaging will be evaluated locally for all patients. For patients with previously documented extramedullary disease or with suspicion of extramedullary progression, a positron emission tomography-computed tomography (PET-CT) scan, computed tomography (CT) scan, or magnetic resonance imaging (MRI) scan will be performed at screening (if the patient has adequate image test performed within 5 weeks of the planned first dose of study drug, they can be used as baseline and do not need to be repeated as part of screening) as needed for evaluation of disease. If extramedullary disease is documented at screening, repeat imaging using the same modality every 12 weeks until a plateau or CR is reached, or as clinically indicated, and then at suspected progression ([Hillengass et al. 2019](#)). A plasmacytoma is considered measurable if the longest diameter is at least 1 cm and the product of the cross diameters is at least 1 cm^2.

Plasmacytomas of lesser size will be considered nonmeasurable. The requirement for bidirectional measurements applies only to plasmacytomas. Imaging tests for patients with extramedullary disease should be performed if new symptoms suggest progressive disease.

All follow-up scans should use the same imaging modality as used at screening.

#### 9.5.13.2 *Bone Imaging*

Imaging will be evaluated locally for all patients. Whole body bone imaging will be performed at screening (if the patient has adequate image test performed within 5 weeks of the planned first dose of study drug, they can be used as baseline and do not need to be repeated as part of screening). Whole body bone imaging can be done using either low-dose total body CT scan or whole body MRI or PET-CT ([Hillengass et al. 2019](#)). A conventional skeletal survey should only be done if other imaging modalities are not available. If there are symptoms or signs that suggest increased or new bone lesions, either whole body bone imaging or localized imaging of symptomatic sites may be repeated any time during the study and at the EOT visit. The same modality for assessment should be used throughout the study.

Patients with no bone disease, or only bone disease at baseline, do not need to repeat imaging periodically unless clinically indicated.

Radiographs will be analyzed locally and reports maintained with the patient record for retrieval during monitoring visits.

#### *9.5.13.3 Quantification of Immunoglobulins*

A blood sample for quantification of immunoglobulins (IgM, IgG, and IgA) will be obtained as specified in [Appendix A](#). For the rare patient with known IgD or IgE MM, the quantitative test for that antibody will be followed at the same time points throughout the treatment period and PFS follow-up period as quantitative immunoglobulins (in addition to quantitative IgM, IgG, and IgA). Analysis of immunoglobulins will be performed locally.

#### *9.5.13.4 Quantification of M-Protein in Serum and Urine*

A blood and 24-hour urine sample will be obtained as specified in the SOE ([Appendix A](#)).

M-protein in serum and urine will be quantified by SPEP and UPEP, respectively. These samples will be tested locally.

#### *9.5.13.5 Serum FLC Assay*

Blood samples will be obtained as specified in [Appendix A](#) for the serum FLC assay (including quantification of  $\kappa$  and  $\lambda$  chains and the  $\kappa:\lambda$  ratio). Blood samples will be analyzed locally.

#### *9.5.13.6 Immunofixation of Serum and Urine*

Serum and urine samples will be obtained as specified in the SOE ([Appendix A](#)) at screening and to confirm a CR. Immunofixation testing will be performed locally.

#### *9.5.13.7 Interference Assay*

IgG mAbs given recently as prior therapy can interfere with assays used to monitor endogenous M-protein. The SPEP and serum immunofixation can be positive due to mAb. This interference can impact the determination of CR and of disease progression in some patients with IgG myeloma protein. Therefore, in patients with persistent VGPR by IMWG criteria where mAb interference is suspected or whenever the SPEP values reach  $\leq 0.2$  g/dL for 2 consecutive disease evaluations during a period of time when the mAb could be circulating at detectable levels, a CR should be suspected triggering the need for interference testing on the M-protein sample at the central laboratory. Currently, if the interference test results are positive, the assay is considered positive for endogenous protein, and thus there is still disease present. If the interference test result is negative, the assay is considered negative for endogenous protein, and thus the remaining protein is likely the mAb. This is communicated back to the sites, and the sites can proceed to perform a confirmatory BMA evaluation for possible CR if not already performed earlier.

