Total serum bilirubin	$\leq 2.0 \times \text{ULN}$ ; an exception for patients with Gilbert's syndrome may be granted after discussion with the sponsor.
Liver transaminases (ALT/AST)	$\leq 3.0 \times \text{ULN}$

ALT: alanine aminotransferase; ANC: absolute neutrophil count; AST: aspartate aminotransferase; ULN: upper limit of normal range.

a Without ongoing growth factor or transfusion support for at least 1 week before Day 1.

8. The minimal interval between the last dose of any of the following treatments/procedures and the first dose of study drug must be at least:

Treatment/Procedure	Minimum Interval
Chemotherapy (including PIs), and IMiDs	14 days
Any investigational anticancer product	28 days or 5 half-lives whichever is longer
Antibody-based anticancer therapy	28 days or 5 half-lives whichever is longer
Corticosteroid therapy for myeloma	7 days
Radiation therapy for localized bone lesions	7 days
Prophylactic localized ("spot") radiation for areas of pain is allowed.	
Major surgery. Patients should be fully recovered from any surgically related complications.	28 days
Plasmapheresis	28 days
Inoculation with any live virus	28 days

PI: proteosome inhibitor; IMiD: immunomodulatory drug.

9. Reproductively female patients who:

- Are postmenopausal for at least 2 years before the screening visit, OR
- Are surgically sterile, OR
- If they are of childbearing potential:
  - Agree to practice 1 highly effective method of contraception and 1 additional effective (barrier) method (see [Table 8.f](#)) at the same time, from the time of signing the informed (e)consent form (ICF) through 3 months after the last dose of daratumumab SC, or 7 days after the last dose of modakafusp alfa, whichever is longer, OR

- Agree to practice true abstinence, when this is in line with the preferred and usual lifestyle of the patient during the entire study treatment period and through 3 months after the last dose of daratumumab SC, or 7 days after the last dose of modakafusp alfa, whichever is longer. (Periodic abstinence [eg, calendar, ovulation, symptothermal, postovulation methods], withdrawal, spermicides only, and lactational amenorrhea are not acceptable methods of contraception. Female and male condoms should not be used together.)
- Agree not to donate an egg or eggs (ova) during the study and for 3 months after the last dose of daratumumab SC, or 7 days after the last dose of modakafusp alfa, whichever is longer.

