### **8.1.2 Combination Agent Daratumumab SC**

#### **8.1.2.1 Dosage**

Daratumumab SC: 1800 mg QW for Cycles 1 and 2, Q2W for Cycles 3 to 6, and Q4W thereafter in 28-day cycles.

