#### 9.5.13.10 *Central Laboratory Evaluations*

##### BMA for MRD

For all patients, a BMA for MRD sample to determine rate and duration of MRD negativity should be collected at screening at the same time as the BMA and biopsy procedure is performed for local disease assessment purposes. Additionally, when a CR is suspected based on laboratory values, per routine clinical practice ([Appendix E](#)), a BMA should be drawn for local disease assessment and central analysis of MRD. Additionally for patients with a confirmed CR, BMAs for MRD should be collected at 6, 12, and 24 months following CR confirmation. If a patient has an MRD[-] result for any of the on-treatment assessments, this will trigger yearly evaluations of MRD, until the patient progresses. However, if a patient does not have an MRD[-] result for any of the planned on-treatment assessments, no additional BMA for MRD will be required. These evaluations will be performed at a central laboratory.

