- ee Following the collection of BMA for MRD sample at screening, an additional 3 mL pull of BMA will be collected for cytogenetic analysis and central evaluation of both tumor and immune fractions of bone marrow. Where country guidelines and/or regulations prohibit genomic analysis, a fluorescent in-situ hybridization will be used to evaluate cytogenetic abnormalities.
- ff Sample collection allowance per country regulations.
- gg It is required that, in addition to blood type (ABO) and Rh typing, the indirect antiglobulin test (also known as Indirect Coombs Test) be performed and the subject carries an identification wallet card with these results at all times during the study.
- hh A portion of this sample may be used [REDACTED].
- ii See Section 9.5.13.7 for details regarding interference testing for patients who received an IgG mAb as recent prior therapy.

[REDACTED]

[REDACTED]

[REDACTED]

- kk Only for patients with test positive for HBV serologies (antibodies to hepatitis B core antigen and/or antibodies to hepatitis B surface antigen) or have a known history of HBV infection. Participants with serologic findings suggestive of HBV vaccination (hepatitis B surface antibody positivity as the only serologic marker) AND a known history of prior HBV vaccination do not need to be tested for HBV DNA by PCR.

**Table 3 Schedule of Events: Screening, Baseline, Cycle 1, and Cycle 2 for Modakafusp Alfa in Combination With Daratumumab SC in the Phase 2a Dose Finding**

Study Period/Cycle	Screening	Cycle 1 (28 d/cycle)				Cycle 2 (28 d/cycle)			
		D1	D8	D15	D22	D1	D8	D15	D22
Day									
Window Allowed	≤21 d	0	±2 d	±2 d	±2 d	±3 d	±3 d	±3 d	±3 d
Informed consent a	X								
Eligibility criteria	X								
Demographics	X								
Medical history	X								
Prior medication and treatment history	X								
Height and weight b	X	X				X			
ECOG performance status	X	X				X			
12-lead ECG c	X	X				X			
Physical examination (may be symptom-directed after screening visit)	X	X	X	X	X	X	X	X	X
Vital signs d	X	X	X	X	X	X	X	X	X
Monitoring of concomitant medication and procedures	Recorded from signing of the ICF through 30 days after last dose of study drug or start of subsequent anticancer therapy, whichever occurs first								
AE reporting	Recorded from signing of the ICF through 30 days after last dose of study drug or start of subsequent anticancer therapy, whichever occurs first (see Section 10.3)								

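### M-protein interference testing is scoped to IgG antibodies from recent prior therapy and does not name study daratumumab, so some complete responses and their linked MRD samples could be missed

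*Protocol*

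**What the plan says.** Protocol Section 9.5.13.7 (Interference Assay) starts from "IgG mAbs given recently as prior therapy can interfere with assays used to monitor endogenous M-protein". It notes that serum electrophoresis and immunofixation may read positive because of the antibody, and that "This interference can impact the determination of CR and of disease progression in some patients with IgG myeloma protein". Central testing is triggered in two situations:

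- persistent VGPR with suspected antibody interference; or
- SPEP at or below 0.2 g/dL at two consecutive evaluations "during a period of time when the mAb could be circulating at detectable levels".

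A negative result means the remaining protein is probably the antibody, and the site may go on to a confirmatory marrow.

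The Appendix A schedules list the interference sample as conditional, (X), from Cycle 2 Day 1 through PFS follow-up. Footnote ii (Tables 1 and 2, phase 1) reads "See Section 9.5.13.7 for details regarding interference testing for patients who received an IgG mAb as recent prior therapy". Footnote hh (Tables 3 and 4, phase 2a) uses the same words.

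Section 7.1, criterion 8, sets the interval since antibody-based anticancer therapy at "28 days or 5 half-lives whichever is longer". Section 8.1.2.1 gives the study antibody as "Daratumumab SC: 1800 mg QW for Cycles 1 and 2, Q2W for Cycles 3 to 6, and Q4W thereafter in 28-day cycles". Section 4.1.3.1 describes daratumumab as IgG1 kappa, and Section 6.1 has it given throughout the study.

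Section 9.5.13.10 asks for the first on-treatment MRD aspirate "when a CR is suspected based on laboratory values", and for later ones at 6, 12 and 24 months after CR is confirmed.

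**The concern.** The test is framed around the antibody least likely to be present and does not mention the one that every patient is receiving. Nowhere do the documents name study daratumumab as a source of M-protein interference. The daratumumab risk text in Section 4.5.2.1 covers only the indirect antiglobulin test, and the SAP does not mention M-protein interference.

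What is at stake is classification within the responders. CR needs negative immunofixation, and MRD sampling depends on CR being suspected or confirmed. If a drug band is not recognised, both can be lost for that patient. MRD[-] CR rate, MRD[-] rate and duration of MRD negativity are secondary endpoints in both phases, and the recommended dose is to be chosen on integrated data that include efficacy (Section 6.1).

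**Working it through.** The plan gives no figure to reproduce here. The check sets the provisions side by side, with two pieces of supporting arithmetic.

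**1. How much prior antibody is left at first dose.** Let T be the half-life and t the time since the last dose. Criterion 8 requires t ≥ max(28 days, 5T). Under first-order elimination the fraction remaining is 0.5^(t/T) ≤ 0.5^5 = 0.03125, so about 3% or less whatever T is.

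**2. How much study antibody is given.** Weekly dosing in Cycles 1 and 2 is 2 × 4 = 8 doses of 1800 mg. Every-2-weeks dosing in Cycles 3 to 6 is 4 × 2 = 8 more, and one dose per cycle follows.

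**3. Who falls outside the footnote.**
- Phase 1: Section 7.1, criterion 4, means every patient has had an anti-CD38 antibody, a class that Section 4.2.1 describes as acting through an IgG1 Fc. Only the undefined word *recent* could exclude them.
- Phase 2a: criterion 5c admits anti-CD38-naive patients. Such a patient with no other recent IgG antibody is outside footnote hh while daratumumab circulates.

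**4. From an omitted test to a lost endpoint.**
- CR requires negative serum and urine immunofixation (Appendix E Table 1). M-protein seen on immunofixation but not on electrophoresis fits the VGPR definition in the same table.
- The first on-treatment MRD aspirate needs a suspected CR. The later scheduled ones need a confirmed CR (Section 9.5.13.10).
- MRD[-] CR rate and MRD[-] rate use the safety population in phase 2a and the response-evaluable population in phase 1. SAP Section 6.1 bases denominators on the population, so an unsampled patient stays in the denominator and the bias is downward.

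**5. Illustration only.** Neither the true CR rate nor the share masked is in the documents. Assume 20 patients in an arm, a true CR rate c of 20% to 50%, and a share m of 10% to 50% of true CRs masked and untested. The observed rate is c(1 − m):

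| c | m = 10% | m = 50% |
|---|---|---|
| 20% | 18% | 10% |
| 30% | 27% | 15% |
| 50% | 45% | 25% |

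At c = 30% and m = 50%, 6/20 (exact 95% CI 0.119 to 0.543) would be reported as 3/20 (0.032 to 0.379).

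**The case against.** The best defence is that the footnotes are cross-references and the operative rule is the trigger in Section 9.5.13.7. Its VGPR limb speaks of suspected antibody interference without saying which antibody. Samples scheduled from Cycle 2 through follow-up also make more sense for an antibody given on study than for one already washed out. This stands as evidence of probable intent. It does not remove the limit. The table notes say that (X) tests are done only in the circumstances given by the attached footnote, and that footnote speaks of prior therapy. In the SPEP limb, the antibody referred to is naturally the one introduced in the section's opening sentence.

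A second defence is that other routes to a marrow remain open. SPEP at or below 0.2 g/dL at two consecutive evaluations is itself a reason to suspect CR. Section 9.5.13.9.1 allows an aspirate at any time on treatment to assess CR, and Section 9.5.13.10 refers to routine practice. This also stands. A positive immunofixation does not by itself close off CR, so the loss is possible, not certain.

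Third, the consequence is bounded. Section 9.5.13.7 confines the effect to some patients with IgG disease. Both phase 2a arms receive the same daratumumab schedule, and no formal comparison is planned. All of this is correct, although the per-arm rates would still be understated.

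A reader might infer that no daratumumab-related test would ever be run, or that both phases are equally exposed. The trigger wording and the phase 1 eligibility rule do not support either reading.

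**Conclusion.** The point holds as a gap in wording with a possible measurement consequence. As written, a site could omit the interference test for a patient whose only circulating IgG antibody is study daratumumab, most clearly an anti-CD38-naive phase 2a patient with IgG myeloma. In some such patients a true CR could be recorded as VGPR and the MRD aspirate not drawn. The CR/sCR categories, MRD[-] CR rate and MRD[-] rate would then be biased downward, and there would be fewer data on duration of MRD negativity.

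The size cannot be computed from the documents; the table above rests on assumed rates. Two shortcuts are unsafe. A reader might take 0.2 g/dL as the level of drug interference, but the protocol uses it only as a trigger for suspecting CR. A reader might also multiply an assumed share of IgG disease by the 40 phase 2a patients, but that counts patients who could be exposed, not CRs missed.

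A reader might further infer that the primary endpoint is compromised. It is largely protected: ORR counts confirmed PR or better (Section 13.1.3.1), and a CR read as VGPR is still a response.

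The conclusion assumes first-order elimination of prior antibody and a site that follows the footnote literally.

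**What to change.** - **Section 9.5.13.7, opening sentence:** widen the scope to IgG antibodies *given as recent prior therapy or as study treatment (daratumumab SC)*, and define *the mAb* in the trigger to match.
- **Same section:** state whether modakafusp alfa, which Section 4.1.2 describes as built on a humanized IgG4 anti-CD38 antibody and which every patient also receives, can interfere, and whether the central assay resolves it. The documents do not say.
- **Footnotes ii and hh:** replace the prior-therapy wording with *any patient meeting the Section 9.5.13.7 triggers*.
- Keep the two existing triggers unchanged.

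The central test and the conditional serum sample are already in the schedules. The cost is the wording change, some additional central test runs, and the CR marrow and MRD samples that the protocol already requires when CR is suspected. If the assay does not resolve modakafusp alfa, that needs separate attention, and its cost cannot be judged from the documents.
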